4.1. Background

Pacemaker-based therapy for atrial fibrillation (AF) has been discussed as an alternative to drugs and ablation for patients with a conventional indication for pacing.^{1,2} Today, many pacemakers and implantable defibrillators include pacing algorithms developed for the prevention or the termination of AF.¹ Most existing pacing algorithms have a preventive nature, designed to suppress AF triggers and to reduce the dispersion of atrial refractoriness that predisposes to re-entry.² Preventive pacing algorithms are primarily designed to decrease premature atrial contractions and prevent pauses, but results of clinical trials with these algorithms have been mixed, probably because of the differences in study design, pacing algorithms and patient populations.³⁻⁶ Anti-tachycardia pacing (ATP) algorithms designed to terminate atrial tachycardia's deliver pacing bursts at a cycle length shorter than that of the detected arrhythmia.^{1,2} While successful ATP could be

observed in terminating atrial flutter or organized atrial tachycardia's, it has proved difficult to interpret the results from clinical studies evaluating ATP for AF.^{1,7,8} Therefore, the evidence of treating AF by pacing is limited, although these algorithms are of interest, since they appear to be safe and usually add little additional cost.^{3,6}

One reason why clinical studies are often non-conclusive, could be that they focus on AF frequency and burden, but few of them are aimed at evaluating the effect of AF pacing on the atrial tissue.⁹ More detail can be found in animal and human mapping experiments: although termination of AF by rapid pacing was not observed, the possibility of creating an area of local capture of the atrial tissue by rapid pacing of AF has been demonstrated.¹⁰⁻¹⁴ To overcome the limitations of human and animal experiments, a computer model of AF has been used to systematically simulate all existing ATP algorithms on AF and test all pacing locations.¹⁵ This systematic model-based testing of site rapid pacing of AF revealed that the septum was the only pacing site that yielded sporadic AF capture episodes in both atria, but this in general did not result in AF termination or permanent changes in AF patterns. Based on this result, a new dual-stage septal pacing has been developed in the computer model: rapid pacing was applied from the septal area following a dual-stage scheme: 1) rapid pacing for 10-30 s at pacing intervals 62-70% of AF cycle length (AFCL), 2) slow pacing for 1.5 s at 180% AFCL, initiated by a single stimulus at 130% AFCL.¹⁶ The proposed septal pacing algorithm could suppress AF reentries in a more robust way than classical single site rapid pacing and at an optimal pacing cycle length (64% AFCL) up to 29% of AF termination was observed in the computer model¹⁶. Septal pacing of AF is therefore proposed here as a simple and attractive approach since it may produce simultaneous bi-atrial stimulation using a single lead, without the need of complex methods for synchronizing multiple pacing sites.

The feasibility of pacing both atria simultaneously from a single lead placed in the interatrial septum has been previously demonstrated clinically¹⁷. These results motivated the testing of atrial septal pacing both as a way to prevent AF occurrence, or to terminate ongoing AF. Clinical studies evaluating the preventive effect of atrial septal pacing have led to mixed results. Becker et al. showed in a canine model that septal pacing produced comparable results as quadruple site pacing in terms of prevention of paroxysmal AF and activation times¹⁸. Kale et al. showed that atrial septal pacing in combination with antiarrhythmic drugs resulted in a subjective improvement of symptoms in patients with drug-refractory paroxysmal AF¹⁹. On the other hand, Hermida et al. showed that atrial septal pacing did not prevent the occurrence of AF²⁰. Hakacova et al. found no significant difference between septal and high atrial preventive pacing, using AF duration and the number of AF episodes as endpoints²¹. A multicenter prospective randomized study by Padeletti et al. showed that preventive pacing of atrial tachycardia's from the septum was associated with a decreased frequency of symptomatic episodes and premature atrial contractions.⁵ In all these studies, safety of interatrial septal pacing was demonstrated. Interest in septal pacing still persists, as is seen in a multicenter parallel randomized study on 380 patients with paroxysmal AF, currently being conducted to evaluate whether septal pacing with or without atrial overdrive pacing could have an effect on AF suppression²².

The AF septal pacing algorithm concept, which is a dual-stage septal pacing scheme (rapid pacing followed by a step-wise transition to slow-pacing) from a ring of stimulation electrodes on the interatrial septum, is described in Figure 2 and in the publication by Uldry et al¹⁶. The septal pacing concept had been developed and tested in a computer model of AF and

in a pig model²³. Experimental studies are now needed to determine whether similar termination mechanisms and efficacies can be observed in humans.

[figure not shown]

Figure 2: Septal-pacing dual-stage pacing scheme: rapid pacing until local capture is achieved, followed by slow pacing, with a step-wise transitions from 130% AFCL (one cycle) to 180% AFCL. Electrodes on the septum should be placed in the area indicated in red (as found in the computer model Luca et al²⁴).

4.2. Purpose

The purpose of this non-randomized, non-controlled, acute, single-arm research study is to evaluate the feasibility to obtain a stable position of a ring of stimulation electrodes on the interatrial septum.

5. Objectives and Endpoints

5.1. Objectives

5.1.1. Primary Objective

The primary objective of the study is to evaluate the feasibility to obtain a stable position of a ring of stimulation electrodes on the interatrial septum.

5.1.2. Secondary Objectives

The secondary objectives of this study are:

- Localized Atrial Capture: evaluate if during the rapid pacing phase of the two-stage septal pacing scheme (rapid pacing followed by a step-wise transition to slow-pacing) from multiple electrodes on the interatrial septum, local atrial capture can be observed during atrial fibrillation.
- AF Termination Scheme: evaluate if AF termination can be obtained using a dual-stage septal pacing scheme (rapid pacing followed by a step-wise transition to slow-pacing) from multiple electrodes on the interatrial septum.

5.2. Endpoints

5.2.1. Primary Endpoint

To assess Pacing Site Stability, the number of interatrial septal pacing electrodes which are successfully placed in a stable position, will be counted. A stable position in this study is defined as a location where the pacing threshold will be < 10 mA at a pacing pulse width of 1 msec. Stable pacing further requires that no ventricular capture will be induced during atrial stimulation at twice the atrial capture threshold.

5.2.2. Secondary Endpoint(s)

To assess Localized Atrial Capture the following endpoints will be considered:

- The number of AF episodes in which local capture is recorded during atrial septal stimulation in at least one of the electrode positions
- The number of electrodes for which local capture is determined using pacing schemes with various pacing cycle lengths (PCL) for a duration of 10-30 seconds depending on when capture occurs, at the start of the scheme followed, if feasible, by slow pacing for 1.5 s at 180% AFCL, initiated by a single stimulus at 130% AFCL.
- The spatial extend of capture (assessed from the atrial electrograms recorded from the multipolar right atrial catheter and the multipolar coronary sinus catheter) to obtain local atrial capture obtained with septal pacing of AF, will be assessed off-line after the study procedure.

To assess whether AF termination can be obtained using a dual-stage septal pacing scheme, the surface ECG will be analyzed and the PCL and stimulation current used will be noted to measure the number of subjects in which the pacing scheme successfully terminates the AF episode.

6. Study Design

The AF Septal Pacing study is a non-randomized, non-controlled, acute, single-arm research study that will be conducted in up to three European centers.

Approximately 15 subjects with AF indicated for ablation of the pulmonary vein will be enrolled in the study. Participants will attend the Baseline visit and the Procedure visit. The baseline visit can be on the same day as the ablation procedure. Since it is an acute study, no follow-up visit will occur. The research procedure will be performed during an already scheduled ablation procedure. Subjects will be enrolled over a period of approximately 18 months.

The point of enrollment is the time when subject signs and dates the Informed Consent Form (ICF). At that point, the subject is considered included in the study.

Selection of subjects, treatment of subjects, and evaluation of study data are potential sources of bias. Methods incorporated in the study design to minimize potential bias include (but are not limited to):

- Patients will be screened to confirm eligibility for enrollment in accordance to the inclusion/exclusion criteria.
- Subject demographics will be collected at baseline on possible differences that may affect the primary objective.
- All study clinicians, participating site personnel, and Medtronic personnel will be trained on their respective pertinent role of the study using standardized training materials.

No control group, no randomization and no blinding will be used in this Study.

6.1. Duration

The expected total study duration is approximately 18 months accordingly to the forecasted enrollment period. Participants will attend the Baseline visit and the Procedure visit (can be on the same day). The results of the study are expected to be ready for internal review approximately 3 months after the last subject visit is completed.

6.2. Rationale

Available literature does not provide a conclusive message on the effect of septal pacing in preventing AF recurrences or suppression of AF. A specific algorithm of pacing the interatrial septal area using a multipolar electrode ring on the intra-atrial septal wall has been designed, with the aim to terminate AF episodes. Following the positive results obtained on a computer model of AF, studies in humans are warranted to obtain information on the feasibility of this pacing strategy.

7. Product Description

7.1. General

All devices used in this clinical study are CE marked and used within the approved indications in the participating countries. The devices will be used to evaluate the feasibility to obtain a stable position of a ring of stimulation electrodes on the interatrial septum. The devices and accessory components that might be used in the study are listed in the below table 1:

Table 1: Devices and accessory components used in AF Septal Pacing

| Component and Model name | Comments | Regulatory Status | Intended Use | Investigational |
|---|--|-------------------|--|--|
| Decapolar Lasso catheter (Biosense Webster, model number Lasso 2515 NAV) | Preferably the Lasso Biosense Webster catheter, since it was used in acute animal studies and positive results were obtained ²³ . Positive results were not obtained with the PVAC and MASC catheter. | CE marked | Indicated for multiple electrode electrophysiological mapping of the cardiac structures of the heart, i.e. recording or stimulation only. The catheter is designed to obtain electrograms in the atrial regions of the heart. (one per subject) | NO (CE marked used within approved indications) |
| Achieve catheter (Medtronic Inc) (single use) (model 990063-020) | In case no stable position can be obtained with the Lasso catheter, we will use the Achieve catheter from Medtronic. | CE marked | Indicated as an intra-cardiac electrophysiology (EP) recording catheter and can be used for cardiac stimulation during electrophysiology studies. (one per subject) | NO (CE marked used within approved indications) |
| EP4 stimulator (St Jude, Minneapolis, USA, model | Or any other four channel electrophysiological stimulator standard | CE marked | Indicated as a cardiac stimulator. (one per site) | NO |

AF Septal Pacing Clinical Investigation Plan

Version 3.0 22-Nov-2017

Page 18 of 49

Medtronic

| Component and Model name | Comments | Regulatory Status | Intended Use | Investigational |
|--|--|-------------------|------------------------------|---|
| number H403023) | used in the EP lab of the hospital. | | | (CE marked used within approved indications) |
| Monitoring catheters: two decapolar mapping electrodes | Any decapolar routinely used in the hospital to monitor signals in right atrium and coronary sinus. | CE marked | Monitoring (one per subject) | NO (CE marked used within approved indications) |
| Monitoring system. | Could be e.g. a stationary Bard EP recording system, a physiological recorder, such as the porti-system (TMSI) or any other electrophysiological monitoring system used in EP lab during the ablation procedure. | CE marked | Monitoring (one per site) | NO (CE marked used within approved indications) |

Pacing system: A clinical electrophysiological stimulator will be used to deliver the dual stage septal pacing protocol to pace and potentially terminate atrial fibrillation. The stimulator should offer four independent pacing channels, to be able to independently stimulate the four electrodes of the interatrial septal catheter. If no four-channel electrophysiological stimulator is available at the clinical study site, study site can request Medtronic reimburse a commercially available four channel electrophysiological stimulator (St. Jude Medical – EP4-Stimulator). The provided stimulator is to be used in accordance with this Clinical Investigation Plan and for this study only.

Pacing catheters: A multipolar (decapolar) Lasso catheters will be used to pace the interatrial septum. In acute animal studies, a Biosense-Webster Lasso Catheter was successfully used²³. Therefore, it is preferable to use the Lasso catheter in this study unless experiences in this human study support the use of another Lasso catheter such as the Achieve. The decapolar Lasso or Achieve catheter will be used according to standard clinical practice.

Monitoring Catheters: Standard electrophysiological recording according to standard clinical practice during AF ablation will be used. This includes the use of a decapolar coronary sinus (CS) electrophysiological recording catheter, and the use of a decapolar right atrial (RA) electrophysiological recording catheter.

Monitoring System: Atrial electrocardiograms will be recorded throughout the study procedure. Intra-atrial electrocardiograms will be recorded from the right atrial decapolar catheter, the coronary sinus catheter and the interatrial septal catheter. All signals will be recorded on the available electrophysiological recording system.

The products needed are already available at the site as standard material used for the routine clinical ablation procedure, for which the patient is indicated and referred to the site.

As a first choice the decapolar Lasso catheter (Biosense Webster, Diamond Bar, USA) will be used. In case this catheter is not effective in the patient, the Achieve catheter (Medtronic) will be used. In case these catheters are not standardly used during the ablation procedure, Medtronic will provide the catheter(s) in accordance with section 7.4.

7.2. Manufacturer of devices

- Decapolar Lasso catheter (Biosense Webster Inc, Diamond Bar, CA, USA)
- Achieve catheter, Medtronic, Inc., [name], USA
- EP4 Stimulator (St Jude Medical, St Paul, MN, USA)

7.3. Intended Population

A sample size of approximately 15 subjects with either persistent and paroxysmal Atrial Fibrillation indicated for the ablation of the pulmonary vein will be enrolled to test if the developed pacing algorithm can terminate AF episodes.

7.4. Equipment

Only in case the participating site didn't have the devices listed in section 7.1 already in its electrophysiological department, the required devices may be provided to the participating study sites by the sponsor upon written request by study site.

In such cases the sponsor, only after site activation and submission of the relative invoice request including supporting documentation, will re-fund the costs related to the purchase of the devices listed in section 7.2 linked to enrolled subjects. Relating to the enrolled study subjects in case the Achieve produced by Medtronic is not used as a standard of care and is needed for the study it will be provided by Medtronic. In case the Lasso produced by Biosense Webster is not used as a standard of care and is needed for the study it will be reimbursed by Medtronic.

In case of need technical support, maintenance and calibration of the study-specific equipment after site delivery will be done by manufacturer representative as per standard agreement between manufacturers and site administration.

Since all devices used during this study are CE marked and used within the approved indication all devices will be labeled in local language, according to local regulation.

7.5. Product Use

For a description of each important component, ingredient, property and principle of operation of the device system/product, including any materials in contact with tissues or body fluids, refer to the relative device Manual.

7.6. Product Training Requirements

Prior to investigation site activation or subsequent involvement in clinical study activities, Medtronic will provide clinical study training relevant and pertinent to the involvement of personnel conducting clinical study activities. As a minimum, investigator responsibilities, Declaration of Helsinki, Clinical Investigation Plan (CIP), ICF, use of data collection tools and applicable local regulations. Study-specific training will be documented prior to investigation site activation or for additional site team members after site activation, prior to them conducting any study-specific tasks.

7.7. Product Storage

Any equipment provided to the site by Medtronic will be stored in a secure location at the site until the end of the procedure of the last enrolled patient.

7.8. Product Return

If applicable at the end of the study the multi-use equipment (EP4 stimulator) provided to the site will be collected by Medtronic personnel and returned to the sponsor.

In case of provision to the site if any of the single use device (Lasso or Achieve catheter) will not be used it will be returned to Medtronic.

7.9. Product Accountability

Each component provided to the site will be traced during the clinical study recording on a specific device tracking log, with the relative serial numbers, with date of receipt, use and final return date to Medtronic. The investigator is responsible for maintenance of each Device Tracking Log (DTL) in the Investigator Site File (ISF). On this log, the receipt,

return and use of the study devices shall be documented. At the end of the clinical study the principal investigator must sign and date the original Device Tracking Logs.

The site will also receive the following study material for the proper conduction to the study:

- Investigator Site File (ISF) to be updated during the study course
- Patient binders

8. Selection of Subjects

8.1. Study Population

Approximately 15 subjects suffering of either persistent and paroxysmal Atrial Fibrillation, indicated for ablation of the pulmonary vein will be enrolled in the study. No control group will be used for this study. The study is planned to be conducted at up to 3 centers in Europe.

In case of missing data of enrolled subject would significantly affect the possibility to properly address study objectives the subject will be replaced in order to have at least 15 complete analyzable subjects' datasets to analyze atrial septal pacing lead stability.

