10.7. Subject Withdrawal or Discontinuation

If a subject is withdrawn from the clinical study, the reason for withdrawal shall be recorded in the study exit form and in the subject's hospital record. If discontinuation is because of safety the subject shall be asked to be followed for collecting safety data outside the clinical study.

Possible reasons for withdrawn from the study are:

- Subject withdrew consent;

- Investigator withdrew subject from the study for medical reasons;
- Investigator withdrew subject from the study due to inclusion/exclusion criteria not met.

Subjects withdrawn might be replaced in case the number of dropouts will significantly affect the possibility to properly address study objectives.

Since AF septal pacing will only be used to collect data only for the time of the clinical study, there is no specific medical care that will be provided to the subjects after the clinical study will be completed or in case of subject withdrawal.

11. Risks and Benefits

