14.2. Patients sets considered for the analysis

The analysis set will include all enrolled patients matching inclusion/exclusion criteria (Intention to Treat).

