8.1 Study Subjects

8.1.1 Disposition of Subjects

The subject disposition will be described in terms of: number of patients enrolled, number of patients undergoing the study stability test, number of patients undergoing the overdrive stimulation test, patients completing the study.

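### Protocol 8.1 lets a subject whose ring could not be positioned or tested be replaced for missing data, and the SAP per-protocol set then leaves that subject out of the feasibility result

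*Protocol*

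**What the plan says.** Protocol 8.1 plans enrolment as "Approximately 15 subjects suffering of either persistent and paroxysmal Atrial Fibrillation, indicated for ablation of the pulmonary vein will be enrolled in the study". It then adds a replacement rule. The condition is "In case of missing data of enrolled subject would significantly affect the possibility to properly address study objectives" and the consequence is "the subject will be replaced in order to have at least 15 complete analyzable subjects' datasets to analyze atrial septal pacing lead stability". The word 'significantly' is not defined, and the rule does not ask why the data are missing.

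Protocol 10.7 has a second rule, for withdrawals: "Subjects withdrawn might be replaced in case the number of dropouts will significantly affect the possibility to properly address study objectives".

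The primary objective (Protocol 5.1.1) is whether a stable ring position can be obtained. Protocol 5.2.1 counts electrodes with a threshold below 10 mA at 1 msec and no ventricular capture at twice the threshold. Protocol 10.3 counts cases, with the threshold criterion met on all electrodes.

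The analysis sets differ between the documents. Protocol 14.2 analyses every enrolled patient who meets the eligibility criteria. SAP 8.1.4, 8.2 and 8.7 use a per-protocol set for the primary and secondary objectives, made up of patients whose septal lead was placed and whose threshold test was carried out. SAP 8.3 leaves missing data out of the analysis, whereas SAP 8.2 says they are included. For disposition, SAP 8.1.1 lists "number of patients enrolled, number of patients undergoing the study stability test, number of patients undergoing the overdrive stimulation test" and the number completing the study.

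**The concern.** When the question is whether something can be done, being unable to do it is a result. Protocol 8.1 allows that result to be handled as missing data.

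This could plausibly arise in two ways. First, Protocol 10.3 repositions the catheter and repeats the tests until ventricular capture no longer occurs. It gives no number of repeats, and Protocol 10.1 expects the study procedure to take about 30 minutes. An attempt abandoned in that loop may leave an incomplete dataset. The SAP field StablePosition (Table 3B) accepts yes, no or na, and no text says which value an abandoned attempt receives. Second, in subjects still in AF after ablation, thresholds and impedances are measured only once sinus rhythm has returned (Protocol 10 and 10.3). If it does not return, there is no sinus-rhythm threshold test, even though the pacing scheme may have been delivered.

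At stake is the denominator of the primary result. The termination result is also affected, because it uses the same per-protocol set: a subject who stays in AF throughout is a non-terminator, and can leave that result for want of a threshold test.

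**Working it through.** **Which subjects are affected.** The rules applied to four situations:

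| Situation | Replaceable under Protocol 8.1 | Protocol 14.2 set | SAP per-protocol set |
|---|---|---|---|
| Tested; threshold 10 mA or more, or ventricular capture | No, data exist | In | In, as a failure |
| Positioning attempted; lead not placed or test not achieved | Yes, if the condition is judged met | In | Out |
| Tested, but values lost (for example a recording fault) | Yes, if the condition is judged met | In | In, but values excluded under SAP 8.3 |
| Still in AF; sinus rhythm not restored | Yes, if the condition is judged met | In | Out, if the test meant is the sinus-rhythm one |

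The second and fourth rows carry the problem.

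**Is there a figure in the plan to reproduce?** No. Protocol 14.1 and SAP 7 state that no sample size calculation was made, so the 15 has no derivation. No failure rate or dropout rate is given.

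**Illustration by counts.** Inputs: 15 complete datasets (Protocol 8.1); s, the number of those with a stable position (assumed); k, the number of attempted subjects replaced because placement or testing failed (assumed). The reported rate is s/15. The all-attempts rate is s/(15 + k). Intervals are exact (Clopper-Pearson) 95%.

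| k | s = 15: reported | s = 15: all attempts | s = 12: reported | s = 12: all attempts |
|---|---|---|---|---|
| 1 | 15/15 = 100% (78.2 to 100) | 15/16 = 93.8% (69.8 to 99.8) | 12/15 = 80.0% | 12/16 = 75.0% |
| 3 | 15/15 = 100% (78.2 to 100) | 15/18 = 83.3% (58.6 to 96.4) | 12/15 = 80.0% | 12/18 = 66.7% |
| 5 | 15/15 = 100% (78.2 to 100) | 15/20 = 75.0% (50.9 to 91.3) | 12/15 = 80.0% | 12/20 = 60.0% |

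**Illustration by rates.** Let f be the assumed share of attempts that fail in a way that leaves no stability data.
- The rate shown is the all-attempts rate divided by (1 - f).
- Expected attempts to reach 15 complete datasets are 15/(1 - f).
- The chance of at least one such failure among the first 15 attempts is 1 - (1 - f)^15.

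| f | An all-attempts rate of 60% appears as | Expected attempts | At least one in the first 15 |
|---|---|---|---|
| 5% | 63.2% | 15.8 | 54% |
| 10% | 66.7% | 16.7 | 79% |
| 20% | 75.0% | 18.8 | 96% |
| 30% | 85.7% | 21.4 | 99.5% |

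If f is zero there is no distortion.

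**The case against.** The strongest reply is that the plan is milder than it may look. Much of that reply stands, and it rules out several stronger readings that a reader might infer.

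- *That every incomplete subject is replaced.* Protocol 8.1 requires that the missing data significantly affect the objectives, and 10.7 uses nearly the same condition. What remains is that the condition is undefined and that a target of 15 complete sets makes it easy to meet. The two rules also differ in force ('will' against 'might').
- *That failures are exchanged for successes.* A measured failure is data and stays in, and a replacement is simply another subject who may also fail. Under 5.2.1 a failed placement could even be read as zero stable electrodes. The documents do not say so.
- *That the result is selected whatever analysis set is used.* Protocol 14.2 would keep the replaced subject. The replacement rule adds a subject and removes nobody. The exclusion comes from SAP 8.1.4 and 8.3.
- *That failures would be invisible.* SAP 8.1.1 shows enrolled against tested numbers, SAP 8.3 reports missing data per variable, and Protocol 10.7 records withdrawal reasons. Attempts, replacements and the reasons for replacement are not listed.
- *That investigators could withdraw a subject because placement went badly.* Protocol 10.7 gives consent withdrawal, medical reasons and unmet criteria as possible reasons. Poor placement is not among them.

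The still-in-AF case concerns what the protocol calls a minority of subjects, and no rate is given for failure to restore sinus rhythm. The study is also purely descriptive, so no test or error rate is affected. None of this settles how an attempted but unachievable placement is counted.

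**Conclusion.** The point holds in a limited form. The combination of Protocol 8.1 and the SAP per-protocol set allows an attempted but unobtainable placement to be replaced and to disappear from the primary result. It also allows a subject who stays in AF to disappear from the termination result. Neither document alone does this, and Protocol 14.2 conflicts with the SAP over who is analysed.

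With all 15 complete subjects successful, one to five replaced failures mean that 100% is reported where 94% to 75% of attempts succeeded. This rests on three assumptions: the SAP set governs the primary result, a failed placement is recorded as untested or missing rather than as not stable, and the condition in 8.1 is judged met. The failure counts are illustrative. The change should be made, because the effect falls on the study's main question, but it is a clarification for a descriptive feasibility study and does not show that the result will be biased.

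**What to change.** 1. Use one rule in Protocol 8.1 and 10.7: a subject may be replaced only if he or she leaves before septal positioning is attempted. State the target as 15 subjects with positioning attempted.
2. Analyse the primary objective on all subjects with positioning attempted. Amend SAP 8.1.4 and 8.7 (and the matching sentence in 8.2), and align them with Protocol 14.2. Count data that are missing because placement or testing could not be achieved as stable position not obtained.
3. Report data missing for unrelated reasons (lost recording, equipment fault, sinus rhythm not restored) as missing, with a sensitivity analysis that counts them as failures. Counting them as failures in the main analysis would bias the result downward. Keep every AF subject who received the pacing scheme in the termination denominator.
4. Reconcile SAP 8.2 with SAP 8.3 on whether missing data are included.
5. Add to SAP 8.1.1 the number attempted and the number replaced, with the reason and the timing relative to the attempt.

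The cost is protocol and SAP wording, two disposition lines and one sensitivity analysis. No more attempted subjects are needed than now. The downside is a possibly lower reported success rate and possibly fewer than 15 complete datasets.
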